3.7.2.6. Columbia-Suicide Severity Rating Scale

The Columbia-Suicide Severity Rating Scale (C-SSRS) will be evaluated at all visits of the

study.

This scale is intended to be used by individuals who have received training in its administration.

The questions contained in the C-SSRS are suggested probes. Ultimately, the determination of

the presence of suicidal ideation or behavior depends on the judgment of the individual

administering the scale.

The interview is semi-structured with a flexible format. Questions are provided as helpful tools

– it is not required to ask any or all questions – just enough to get the appropriate answer.

Most important: gather enough clinical information to determine whether patient is suicidal or

not. If it is established that a patient has not engaged in any suicidal behavior and/or ideation,

then no further questions are required.

3.7.2.7. Withdrawal symptoms

A specific questionnaire provided 1 week after discontinuation of the study drug will investigate

Confidential

63

Version 3.0 September 30th, 2020

the possible occurrence and pattern of amphetamine like withdrawal symptoms (DSM-IV) which are defined as dysphoria and two or more of the following symptoms: fatigue, vivid and unpleasant dreams, insomnia or hypersomnia, increased appetite and psychomotor retardation or agitation.

4. INVESTIGATIONAL TREATMENT

4.1. DESCRIPTION OF STUDY TREATMENT: BF 2.649

, HCl

4.1.1. Chemical structure

BF2.649 (pitolisant) is 1-{3-[3-(4-chloro-phenyl)-propoxy]-propyl}-piperidinium, hydrochloride.

STRUCTURAL FORMULA

BF2.649
$$N-(CH_2)_3-O-(CH_2)_3-C$$

MOLECULAR FORMULA

RELATIVE MOLECULAR MASS

4.1.2. Composition and form of investigational treatments

The investigational treatments (BF2.649 5 mg and placebo) are provided in film-coated tablets, white, round, of 3.7 mm diameter engraved "5" on one side. BF2.649 5 mg and placebo tablets are identical in appearance (form, dimension and color) to maintain the blind.

The investigational treatment (BF2.649 20 mg and placebo) are provided in film-coated tablets, white, round, of approximately 7,5 mm in diameter, engraved "20" on side. BF2.649 20 mg and placebo tablets **are identical in appearance** (form, dimension and color) to maintain the blind.

The ingredients of unitary BF2.649 tablets are described in the table below:

Placebo tablets will contain only lactose to ensure that neither the patient nor the investigator nor members of the clinical staff know the identity of the study medication.

4.2. **DOSAGE REGIMEN**

Following the completion of inclusion procedures, patients will start pitolisant (BF2.649) treatment with escalating doses scheme as follows:

- -V2 (D0):
- Week 1: BF2.649 at 5 mg/day: 1 tablet of BF2.649 5 mg or placebo in the morning during 7 days.
- Week 2: BF2.649 at 10 mg/day: 2 tablets of BF2.649 5 mg or placebo in the morning during 7 days.
 - $-V3 (D14\pm 2)$:
- Week 3: according to the investigator's prescription patients for whom the optimal dose level is estimated will continue at the same dose or if not sufficiently improved in their symptoms, and with a good tolerance, will increase to a higher dose or the level dose will be reduced based on the tolerance to the product.

BF2.649 at 5 mg/day: 1 tablet of BF2.649 5 mg or placebo in the morning during 7 days, or BF2.649 at 10 mg/day: 2 tablets of BF2.649 5 mg or placebo in the morning during 7 days, or BF2.649 at 20 mg/day: 1 tablet of BF2.649 20 mg or placebo in the morning during 7 days.

BIOPROJET Protocol P11-06/ BF2.649 EudraCT number: 2013-001506-29

- $-V4 (D21\pm 2)$:
- Week 4: according to the investigator's prescription patients for whom the optimal dose level is estimated will continue at the same dose or if not sufficiently improved in their symptoms, and with a good tolerance, will increase to a higher dose or the level dose will be reduced based on the tolerance to the product.

BF2.649 at 5 mg/day: 1 tablet of BF2.649 5 mg or placebo in the morning during 7 days, or BF2.649 at 10 mg/day: 2 tablets of BF2.649 5 mg or placebo in the morning during 7 days, or BF2.649 at 20 mg/day: 1 tablet of BF2.649 20 mg or placebo in the morning during 7 days, or BF2.649 at 40 mg/day: 2 tablets of BF2.649 20 mg or placebo in the morning during 7 days. Treatment dosage at 40mg/day not allowed for patient with a weight less than 40 kg.

- -V5 (D28±2): No increase of BF2.649 dosage will be authorized, but it will be possible to decrease the dose, if the tolerance requires it. From this visit onwards, no dose change will be allowed.
- Week 5 to week 8: according to the investigator's prescription patients for whom the optimal dose level is estimated will continue at the same dose or the level dose will be reduced based on the tolerance to the product.

BF2.649 at 5 mg/day: 1 tablet of BF2.649 5 mg or placebo in the morning during 28 days, or BF2.649 at 10 mg/day: 2 tablets of BF2.649 5 mg or placebo in the morning during 28 days, or BF2.649 at 20 mg/day: 1 tablet of BF2.649 20 mg or placebo in the morning during 28 days, or BF2.649 at 40 mg/day: 2 tablets of BF2.649 20 mg or placebo in the morning during 28 days. Treatment dosage at 40mg/day not allowed for patient with a weight less than 40kg.

- V7 (D56± 2): Prescription of 1-week of placebo for all patients.

In open-label period patients will start pitolisant treatment with escalating doses scheme, as follows:

- V8 (D63 \pm 2)
- Week 10: BF2.649 at 5 mg/day: 1 tablet of BF2.649 5 mg in the morning during 7 days.
- Week 11: BF2.649 at 10 mg/day: 2 tablets of BF2.649 5 mg in the morning during 7 days.
 - $-V9 (D77\pm 2)$:
- Week 12: according to the investigator's prescription patients for whom the optimal dose level is estimated will continue at the same dose or if not sufficiently improved in their symptoms, and with a good tolerance, will increase to a higher dose or the level dose will be reduced based on the tolerance to the product.

BF2.649 at 5 mg/day: 1 tablet of BF2.649 5 mg in the morning during 7 days, or

EudraCT number: 2013-001506-29

BF2.649 at 10 mg/day: 2 tablets of BF2.649 5 mg in the morning during 7 days, or BF2.649 at 20 mg/day: 1 tablet of BF2.649 20 mg in the morning during 7 days, or

 $-V10 (D84\pm 2)$:

- From Week 13: according to the investigator's prescription patients for whom the optimal dose level is estimated will continue at the same dose or if not sufficiently improved in their symptoms, and with a good tolerance, will increase to a higher dose or the level dose will be reduced based on the tolerance to the product.

BF2.649 at 5 mg/day: 1 tablet of BF2.649 5 mg in the morning during 28 days, or

BF2.649 at 10 mg/day: 2 tablets of BF2.649 5 mg in the morning during 28 days, or

BF2.649 at 15 mg/day: 3 tablets of BF2.649 5 mg in the morning during 28 days, or

BF2.649 at 20 mg/day: 1 tablet of BF2.649 20 mg in the morning during 28 days, or

BF2.649 at 30 mg/day: 2 tablets of BF2.649 5 mg and 1 tablet of BF2.649 20 mg in the morning during 28 days, or

BF2.649 at 40 mg/day: 2 tablets of BF2.649 20 mg or placebo in the morning during 28 days. Treatment dosage at 40mg/day not allowed for patient with a weight less than 40 kg.

At D91 during the phone contact the dose will be reduce in case of poor tolerance, when applicable.

$-V11 (D112\pm 2)$:

According to the investigator's prescription patients for whom the optimal dose level is estimated will continue at the same dose or if not sufficiently improved in their symptoms, and with a good tolerance, will increase to a higher dose or the level dose will be reduced based on the tolerance to the product.

BF2.649 at 5 mg/day: 1 tablet of BF2.649 5 mg in the morning during 3-month, or

BF2.649 at 10 mg/day: 2 tablets of BF2.649 5 mg in the morning during 3-month, or

BF2.649 at 15 mg/day: 3 tablets of BF2.649 5 mg in the morning during 3-month, or

BF2.649 at 20 mg/day: 1 tablet of BF2.649 20 mg in the morning during 3-month, or

BF2.649 at 30 mg/day: 2 tablets of BF2.649 5 mg and 1 tablet of BF2.649 20 mg in the morning during 3-month, or

BF2.649 at 40 mg/day: 2 tablets of BF2.649 20 mg or placebo in the morning during 3-month. Treatment dosage at 40mg/day not allowed for patient with a weight less than 40 kg.

 $-V12 (D196\pm 2)$:

According to the investigator's prescription patients for whom the optimal dose level is Confidential 68

estimated will continue at the same dose or if not sufficiently improved in their symptoms, and with a good tolerance, will increase to a higher dose or the level dose will be reduced based on the tolerance to the product.

BF2.649 at 5 mg/day: 1 tablet of BF2.649 5 mg in the morning during 6-month, or

BF2.649 at 10 mg/day: 2 tablets of BF2.649 5 mg in the morning during 6-month, or

BF2.649 at 15 mg/day: 3 tablets of BF2.649 5 mg in the morning during 6-month, or

BF2.649 at 20 mg/day: 1 tablet of BF2.649 20 mg in the morning during 6-month, or

BF2.649 at 30 mg/day: 2 tablets of BF2.649 5 mg and 1 tablet of BF2.649 20 mg in the morning

during 6-month, or

BF2.649 at 40 mg/day: 2 tablets of BF2.649 20 mg or placebo in the morning during 6-month. Treatment dosage at 40mg/day not allowed for patient with a weight less than 40 kg.

- All subsequent visits, the treatment dispensation will be done as V12.

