- 13) Active clinically significant illness, including unstable cardiovascular, endocrine, neoplastic, gastrointestinal, haematological, hepatic, immunologic, metabolic, neurological (other than narcolepsy/cataplexy), pulmonary, and/or renal disease which could interfere with the study conduct or counter-indicate the study treatments or place the patient at risk during the trial or compromise the study objectives.
- 14) Prior severe adverse reactions to CNS stimulants.
- 15) Known hypersensitivity to the tested treatment including active substance and excipients.
- 16) The inability to continue daily activities safely, without the use of treatment against EDS.
- 17) Any patient presenting congenital galactosemia, glucose-galactose malabsorption or lactase deficiency due to the presence of lactose in investigational treatments.
- 18) Patients participating in another study or being in a follow–up period for another study.
- 19) Cannot be contacted in case of emergency.

Dosage, treatment regimen, route of

Starting dose of 5 mg, increasing to a maximum oral dose of 20 or 40 mg once daily, according to efficacy, tolerability and patient weight.

Patients with a weight less than 40kg will be treated with a maximum daily

Ludiaci ilumber. 2013-00							
administration	dose of to 20mg.						
	Treatment taken the morning before breakfast.						
Control(s)	Placebo						
Primary efficacy endpoint	Change in the intensity and frequency of symptoms of narcolepsy (EDS and cataplexy) as measured by the Ullanlinna Narcolepsy Scale (UNS) between baseline: [V1 score (D-14) + V2 score (D0)]/2 and the end of treatment: [V6 score (D49) + V7 score (D56)]/2. We will compare the results between pitolisant and placebo groups.						
	- Changes in EDS as measured by the maintenance of wakefulness test (MWT) between baseline and V7, in pitolisant and placebo groups.						
	- Change in EDS measured by the Paediatric Daytime Sleepiness Scale (PDSS) between baseline: [V1 score (D-14) + V2 score (D0)]/2 and the end of treatment: [V6 score (D49) + V7 score (D56)]/2. We will compare the results between pitolisant and placebo groups.						
	- Changes in EDS as measured by the Child and Adolescent Sleepiness Scale (CASS) between baseline and the end of treatment, in pitolisant and placebo groups.						

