- 13) Active clinically significant illness, including unstable cardiovascular, endocrine, neoplastic, gastrointestinal, haematological, hepatic, immunologic, metabolic, neurological (other than narcolepsy/cataplexy), pulmonary, and/or renal disease which could interfere with the study conduct or counter-indicate the study treatments or place the patient at risk during the trial or compromise the study objectives.
- 14) Prior severe adverse reactions to CNS stimulants.
- 15) Known hypersensitivity to the tested treatment including active substance and excipients.
- 16) The inability to continue daily activities safely, without the use of treatment against EDS.
- 17) Any patient presenting congenital galactosemia, glucose-galactose malabsorption or lactase deficiency due to the presence of lactose in investigational treatments.
- 18) Patients participating in another study or being in a follow-up period for another study.
- 19) Cannot be contacted in case of emergency.

STUDY TREATMENT

Patients will be outpatients followed in ambulatory way during the whole study period and they will all receive the investigational study treatment pitolisant or placebo as described § 4.2. Patients will be asked to take the study drug every day before breakfast, according to the investigator's prescription regarding the dose regimen of patients, based on the product efficacy

and tolerance.

The total treatment duration of this double blind study is 8 weeks. Patients will start pitolisant treatment with escalating doses scheme on the first 4 weeks, as follows:

- V2 5 mg of BF2.649 or placebo / day during the first week,
 - 10 mg of BF2.649 or placebo /day during the second week,
- V3 Increase to 20 mg/d or maintain at 10 mg/d or reduce to 5 mg/d of BF2.649 (or placebo) per day for 7 days depending on efficacy and tolerability.

- V4 It will also be possible to reduce the dose administered to the patients, or to increase it without exceeding 40 mg/d. Patients with a weight less than 40kg could be treated with a maximum daily dose of 20mg.
- V5 It will be possible to reduce the dose administered to the patients, but not to increase it.
 - As from V5 onwards, no dosage change of the study treatment will be authorized.
- At the end of the double blind treatment (V7), the investigator will provide placebo to all patients for the one-week wash out period.

In open-label period patients will start pitolisant treatment with escalating doses scheme, as follows:

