- V8 5 mg of BF2.649 or placebo / day during the first week.
 - 10 mg of BF2.649 or placebo /day during the second week.
- V9 The third week according to investigator prescription and evaluation on efficacy and tolerance, the dose will be maintained or increased at 20 mg/d or reduced at 5 mg/d.
- V10 According to investigator prescription and evaluation on efficacy, tolerance and weight, the dose will be maintained, reduced or increased at 5, 10, 15, 20, 30 or 40 mg/d (only if patient weight is above 40kg) for the next 4-week During the phone contact (T2), in opinion of investigator, the dose could be readjusted according the effectiveness/tolerability of treatment to patient. In case of need, it is possible to plan a visit on site within the week following phone contact for obtaining new bottles of treatment with the corresponding dose.
- V11 According to investigator prescription and evaluation on efficacy, tolerance and weight, the dose will be maintained, reduced or increased at 5, 10, 15, 20, 30 or 40 mg/d (only if patient weight is above 40kg) for the next 3-month.
- V12 According to investigator prescription and evaluation on efficacy, tolerance and weight, the dose will be maintained, reduced or increased at 5, 10, 15, 20, 30 or 40 mg/d (only if patient weight is above 40kg) for the next 6-month.
- All subsequent visits, the treatment dispensation will be done like V12.

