5.2.13. V10- Dose adjustment visit (Day 84 ± 2 days)

Idem to the visit V9.

Investigational treatment allocation: the dose of pitolisant will be individually adjusted

according to the investigator's prescription.

A blood sample will be taken for routine haematological and biochemical test (including β-

HCG pregnancy test for pubescent female) and semi-quantitative urinalysis (dipstick),

Dose allocation: either 5, 10, 15, 20, 30 or 40 mg/day or placebo in the morning during 28 days.

Patients with a weight less than 40 kg could be treated with a maximum daily dose up to 20 mg.

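### Open-label dosing in section 4.2 bars only 40 mg/day below 40 kg and leaves the 30 mg step open, although the protocol elsewhere caps these children at 20 mg/day

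*Protocol*

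**What the plan says.** The protocol states the weight limit in four places, in three different forms.

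- **Synopsis, dosage row.** The rule is split by the table layout but readable: "Patients with a weight less than 40kg will be treated with a maximum daily" and then "dose of to 20mg". It is not limited to one study period.
- **Sections 5.2.13 to 5.2.16 (V10, V11, V12, and V13 with later visits).** Each gives the open-label dose list, including 30 mg, and follows it with "Patients with a weight less than 40 kg could be treated with a maximum daily dose up to 20 mg".
- **Section 4.2, open-label V10, V11 and V12.** The dose list includes "BF2.649 at 30 mg/day: 2 tablets of BF2.649 5 mg and 1 tablet of BF2.649 20 mg", with no weight condition attached. The list ends with "Treatment dosage at 40mg/day not allowed for patient with a weight less than 40 kg". After V12 comes "All subsequent visits, the treatment dispensation will be done as V12", so the same rule runs on.
- **Section 3.5, open-label V10 to V12.** The dose is "increased at 5, 10, 15, 20, 30 or 40 mg/d (only if patient weight is above 40kg"), with the weight condition in brackets at the end of the list.

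Section 3.5 also says of the patients that "they will all receive the investigational study treatment pitolisant or placebo as described § 4.2", which makes section 4.2 the referenced dosing section. Section 4.2 is also where the tablet counts are given.

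**The concern.** A paediatric dose ceiling should read the same wherever a site might look it up. Here the section that gives tablet counts, and to which section 3.5 refers, rules out one dose for children under 40 kg, while the synopsis and the visit sections rule out two. No clause sets an order of precedence. A pharmacist or investigator working from section 4.2 could dispense 30 mg/day to a child under 40 kg and find nothing in that section against it.

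The question comes back at every dispensing, because open-label treatment continues until the drug is marketed for children or the patient reaches 18. Section 5.2.18 also allows dose adjustment by telephone and home shipment during the pandemic, when a clear written rule matters more. The SAP covers only the blind part (SAP sections 2 and 3.2), so no analysis planned in these documents would bring such a dose to light.

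**Working it through.** This is a comparison of texts with simple arithmetic.

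**Highest dose left for a child under 40 kg, by section**

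| Place | Dose levels (mg/day) | Weight rule below 40 kg | Highest level left |
|---|---|---|---|
| Section 4.2, double-blind V4 and V5 | 5, 10, 20, 40 | 40 mg barred | 20 mg |
| Section 4.2, open-label V9 | 5, 10, 20 | none needed | 20 mg |
| Section 4.2, open-label V10, V11, V12 and later | 5, 10, 15, 20, 30, 40 | 40 mg barred | 30 mg |
| Sections 5.2.13 to 5.2.16 | 5, 10, 15, 20, 30, 40 | maximum 20 mg | 20 mg |
| Synopsis, dosage row | not listed in that row | maximum 20 mg | 20 mg |

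The first row suggests how the gap arose. In the double-blind period 40 mg is the only level above 20 mg, so barring 40 mg and capping at 20 mg come to the same thing. The open-label list adds 15 and 30 mg, but section 4.2 keeps the double-blind sentence.

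**Section 3.5.** The bracketed weight condition follows 30 or 40 mg. It can be read as qualifying 40 mg alone, which agrees with section 4.2, or both doses, which agrees with section 5.2. It does not settle the matter by itself.

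**Size of the difference**

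- The 30 mg step is 2 × 5 + 1 × 20 = 30 mg.
- Ratio to the cap: 30 / 20 = 1.5. Excess: 30 − 20 = 10 mg/day.
- Interval covered by one dispensing, from the scheduled visit days, and excess if 30 mg is taken throughout:
  - V10 (day 84) to V11 (day 112): 28 days, 28 × 10 = 280 mg
  - V11 (day 112) to V12 (day 196): 84 days, 84 × 10 = 840 mg
  - V12 (day 196) to V13 (day 364): 168 days, 168 × 10 = 1,680 mg

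**Dose per kilogram.** The documents give no weight distribution, so the weights below are assumed.

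| Weight (kg) | 20 mg (mg/kg/day) | 30 mg (mg/kg/day) |
|---|---|---|
| 20 | 1.00 | 1.50 |
| 25 | 0.80 | 1.20 |
| 30 | 0.67 | 1.00 |
| 39 | 0.51 | 0.77 |

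For comparison, 40 mg at 40 kg, the lightest weight not covered by the 20 mg cap, is 40 / 40 = 1.00 mg/kg/day.

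**The case against.** The strongest reply is that section 4.2 is silent and does not grant anything. A child under 40 kg held at 20 mg complies with every section at once, so the rules can be followed together. The cap also stands where the visit is run: each of sections 5.2.13 to 5.2.16 puts it directly after the dose list. Section 3.5 itself gives the 20 mg figure at V4. Read with the synopsis and section 5.2, the bracket in section 3.5 makes sense only if it covers both 30 and 40 mg. On this view the intent is plain.

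The consequence can also be overstated. The cumulative milligrams are just 10 mg times days and have no safety meaning of their own. At 30 to 39 kg, 30 mg gives 0.77 to 1.00 mg/kg/day, no more than the protocol accepts at 40 mg and 40 kg. Only children under 30 kg would exceed that figure, and the documents name no hazard specific to 30 mg at these weights.

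Most of this stands, and it limits the weight of the point. It does not close the gap. The intent has to be pieced together from other sections, while the section given as the dosing reference states an incomplete rule. The V4 line in section 3.5 belongs to the double-blind period. The cap is an absolute dose, so a per-kilogram comparison does not make 30 mg compliant with it.

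**Conclusion.** The inconsistency is real and should be corrected. From V10 onward, section 4.2 excludes only 40 mg/day for children under 40 kg, so the highest level it leaves open is 30 mg/day, against the 20 mg/day maximum in the synopsis and sections 5.2.13 to 5.2.16. The excess is 10 mg/day, or half the cap again. This rests on the current wording and needs no assumption beyond a reader relying on section 4.2 alone.

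It is a dosing-safety and clarity matter in the open-label period only. Double-blind doses, sample size and the primary analysis are untouched. Whether any child has received 30 mg below 40 kg, and with what consequence, cannot be judged from the documents.

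**What to change.** The 20 mg cap should govern, since the synopsis and all four visit sections state it. No new dosing decision is needed.

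1. In section 4.2 at V10, V11 and V12, and so at later visits, replace the sentence barring only 40 mg with: *Patients weighing less than 40 kg: maximum 20 mg/day; 30 and 40 mg/day not allowed.*
2. In section 3.5 at the same three visits, state that both 30 and 40 mg/day require a weight of at least 40 kg. This also settles the case of exactly 40 kg, which section 3.5 now excludes by asking for a weight above 40 kg, while the other sections restrict only weights below it. Declare it as a separate edit.
3. Notify the sites by letter.
4. Produce one listing of open-label dose against the body weight at that visit, to find any dose above 20 mg given below 40 kg. Where a telephone visit replaced a site visit, use the last recorded weight.

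The cost is a wording change at three visits in each of two sections, a letter and one listing. Quantities dispensed (section 4.6) and body weight at each visit (section 6.1.1) are already recorded.

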4.3. PACKAGING AND LABELLING OF TREATMENT

The medications will be supplied, packaged and labelled in compliance with the Good Manufacturing Practices (GMP) appendix 13 of drugs and ICH of used in clinical trial.

Each label will be labelled in the local language of the investigational centre.

Each treatment unit will contain the study medication for all the duration of the study, i.e. 9 weeks.

